Short version of the final protocol

(Ver 6, Aug 31, 2018)

Introduction

Every year more than 250,000 patients are admitted in the Capital Region of Denmark. During admissions, the clinical track and trigger system "Early Warning Score (EWS)" is used to systematically observe and detect acutely deteriorating patients. The system is designed to prevent serious adverse events like unanticipated transfer to the intensive care unit, cardiac arrest and unexpected death. EWS consists of standardized measurements of the patient's vital signs and an escalation protocol that determines further actions based on the aggregated EWS score. At admission, and as a minimum twice a day, nurses measure vital signs on all hospitalized patients. Depending on the predetermined cut-off values (i.e. heart rate above 150 bpm = 3 points) an aggregated score is calculated. Based on the total score, the escalation protocol determines the time interval for the next measurement as well as a clinical action (i.e. call for attending doctor). EWS is developed to detect and to treat potentially deterioration of disease that might lead to critical illness and death. In its current form, there is only limited room for individual clinical assessment. A standardized track and trigger system like EWS does not differentiate between different types of disease or the patient's individual physiological response. Therefore, there is a potential risk that the system fails to detect a patient with an abnormal stress response. Additionally; patients suffering from chronic illness might have different normal values than healthy patients, leading to unnecessarily excess observation, measurement, and suboptimal usage of limited staff resources.

Further improvement and optimizing of the EWS track and trigger system is necessary, as there is potential to improve patient care and use staff resources more appropriate. The current study will examine the effect of a new Individual EWS (I-EWS) with incorporated clinical assessment using the staff's professional experience and providing even more personalized observation and treatment.

Aim of the study

The aim of the study is to investigate the impact of the I-EWS that has a systematic involvement of clinical assessment and the possibility to adjust the score, whilst keeping the same escalation protocol. I-EWS will be compared to the existing EWS with a focus on mortality, critical illness, and the use of staff resources.

Hypothesis

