The main hypothesis is that I-EWS will be non-inferior to the existing NEWS algorithm regarding 30-day mortality, but the introduction of clinical assessment results in fewer I-EWS scores per patient per day than with NEWS.

Method

The study is a prospective, cluster randomized, cross-over, non-inferiority study. The participating eight hospitals are randomly assigned to six and a half months with either I-EWS or the existing EWS track and trigger system. Computer generated numbers are used to randomize the hospitals to either the intervention or control arm of the study. A single cross-over will take place resulting in a total study period of 13 months. I-EWS is only available at hospitals assigned to I-EWS (Grey areas in the figure below). All EWS scores and subsequent actions are documented in real time. Each period will start with 14 days of implementation, and before cross-over patients will be followed by an observation period of 30 days (indicated by shaded areas below).

Hospital	1 period: 6 ½ months	2. period: 6 ½ months
Herlev & Gentofte Hospital (2 units)	Cluster 1	Cluster 1
Amager og Hvidovre Hospital (2 unit)	Cluster 2	Cluster 2
Nordsjællands Hospital (2 units)	Cluster 3	Cluster 3
Bispebjerg Hospital (1 unit)	Cluster 4	Cluster 4
Glostrup Hospital (1 unit)	Cluster 5	Cluster 5
Sjællands Universitetshospital (2 units)	Cluster 6	Cluster 6
Slagelse Hospital (1 unit)	Cluster 7	Cluster 7
Holbæk Hospital (1 unit)	Cluster 8	Cluster 8

Intervention: Prior to project start ambassadors from all the participating wards will receive 2 hours of education depending on which EWS their hospital is randomized to use. Hospitals randomized to use I-EWS will receive an introduction course and hospitals using EWS will receive a brush-up course. Subsequently, they will be responsible for teaching at their respective wards. I-EWS, like the current EWS, will apply systematic observation, where patients continue to be evaluated according to vital signs and assigned a score of 0-20. The innovation in I-EWS is that SP systematically calls for staff to reassess the assigned score after they have entered the patient's vital signs. Afterwards it is possible to adjust the score by a maximum of +6 or -4. Nursing staff reevaluate when vital signs and clinical assessment are compared, whether the patient is in the correct observation range, and if the clinical actions defined for this range is relevant.

Ethics

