- 1. ≥18 years at admittance at participating hospital
- 2. Admittance in a department/Ward using systematised EWS
- 3. Admittance for more than 24 hours

Patients will be included at the first admission in the study period (index admission) and will remain in this group (intervention/control) for a follow-up period of 30 days. All subsequent admissions (readmissions) will be ignored.

Exclusion

- 1. Patients arriving at the gynaecological-, obstetric-, and paediatric department
- 2. If a "do not resuscitate"-order or "no NEWS/I-EWS registration" are identified, patients will be excluded for further analysis at the time of registration.

Definition of clusters

Eligible hospitals can consist of one or two units. A hospital is defined based on its administrative organisation and catchment area. Each hospital will generate one cluster and two (time) periods (control and intervention). See schematic figure 1 below

Randomisation

Prior to the study start participating clusters will be randomised to start as either intervention or control. Eight cluster will be available, and we will be using stratified randomisation based on size of hospitals (number of unique admissions, more than 25,000 admissions is defined as large hospitals, less than 25,000 is small hospitals), to balance a potential size difference between the intervention and control group. The randomization will be performed using computer-generated numbers. The randomisation will allocate participating hospitals to periods of intervention or control in a 1:1 ration. A cross-over will occur after 6.5 months and is expected to be at April 15, 2019.

Ethics

The study was presented to the Regional Ethics Committee, who decided that no formal approval was needed in accordance with Danish law (J.nr. 1701733). Data management has been approved by the Danish Data Protection Agency (ID: HGH-2017-116, I-suite:06030).

Study variables:

The following data are collected as a minimum for the included patients:

- Age and gender
- Personal Identification number (Danish Civil Registration number (CPR)

- Presence of Do Not Resuscitate (DNR) order
- Presence of "No EWS registration"
- EWS/I-EWS Scores
- Registered actions to the EWS/I-EWS escalation protocol
 - Responsible nurse contacted
 - Treatment plan already made
 - Doctor contacted
 - MET contacted
 - Other
 - Charlson Comorbidity Index

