At follow-up (30 days after inclusion of last patient) the following data is collected from the National Patient Registry (NPR) and the electronic patient journal system Sundhedsplatformen:

- Contacts with the hospital system (including all historical contacts).
- Information regarding admissions (date, time and place of admission and discharge).
- Diagnoses (follow-up during study period, historical and in relation to index admission).
- Date of death or emigration (only very few cases of emigration are expected).

Sundhedsplatformen, hospital based local databases, and clinical databases (such as DANARREST) will provide data on:

- Registered Cardiac arrest
- MET activation

Endpoints

The primary endpoint;

• All-cause mortality at 30 days

Co-primary endpoint;

• The number of NEWS/I-EWS scores per patient per day

The secondary endpoints;

- Length of hospital stay
- All-cause mortality at 2 days

• All-cause mortality at 7 days

Additionally, the following will be reported;

Use of EWS / I-EWS;

- Frequency of changes in I-EWS scores that lead to an escalation or de-escalation in the escalation protocol
- Comparison of changes in EWS score due to I-EWS modification (intervention group) and due to temporary or chronic acceptable values (control group)
- The number of Cardiac arrests* during hospital stay, reported in numbers (%) and per 10,000 ward days
- Scores generating a call for Mobile Emergency team (MET) reported in absolute number (%) and per 10,000 ward days
- Scores generating calls for the attending doctor, reported in absolute number (%) and per 10,000 ward days

*Definition – Presence of a clinical cardiac arrest (as defined in the resuscitation guidelines) in patients without a DNAR (Do Not Attempt Resuscitation) order. Registered in DANARREST.

Sample size calculation

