In addition to the ITT analysis, a per-protocol analysis will be performed. In this analysis, interventional patients with missing or incomplete (missing a I-EWS modification in more than 1/3 of the total number of measurements) I-EWS measurement will be excluded. Finally, a sensitivity analysis will be performed, where patients that are transferred between hospitals will be excluded. Sensitivity analyses will be performed for the last three months of each intervention period and excluding departments where I-EWS protocol was not followed.

Subgroup analyses of primary endpoint

The primary outcomes will be calculated for the following subgroups, including a test for interactions: Age (\leq 39 years, 40 to 69 years, \geq 70 years), admissions at defined cluster, and according to the primary discharge diagnosis; cardiovascular disease, infections, pulmonary disease neurological disease, cancer and surgery done during admission. Results will be presented graphically using a forest plot.

Secondary endpoints

Secondary endpoints regarding mortality will be analysed using the same analysis as the primary endpoint. Length of hospital stay between groups will be compared by linear regression following the same adjustment principles as for the primary outcome.

Additional measurements

The frequency of changes in I-EWS that led to an escalation or de-escalation in the escalation protocol will be reported. Changes in NEWS due to CROS values and changes in I-EWS due to clinical assessment will be compared using Poisson regression models.

Handling of missing data

The primary outcome analysis should be subject to no or little missing data as it is based on Danish register data. Patients lost to follow-up (tourists) will be censored at the last registration.

Handling of diagnoses for outcome and subgroups

Diagnoses obtained from the National Patient Registry are coded with the ICD-10 system. The original chapters will be used to group patients according to diagnoses. The primary diagnosis will be used when constructing. The following will define the subgroups: **Cancer:** Chapter II: Neoplasms (C00-C97 + D37-D48). **Cardiovascular disease:** Chapter IX: Diseases of the circulatory system (I09-I52 + I70-I89)

Pulmonary disease: Chapter X: (DJ00-DJ99)

Infections: Chapter I: (A00-B99 + J00-J22 + N10-N11+ N30-N31 + G00-G09)

Neurological disease: Chapter VI: Diseases of the nervous system (G09-G47 + I60-I69)

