Surgical conditions: Presence of surgical procedure codes divided into different specialties (general, orthopedic, other)

Hospital	Unique admission in 2016	Death within 30 days
Herlev & Gentofte Hospital (2 units)	41.420	1122 (2.64 %)
Amager & Hvidovre Hospital (2 unit)	26.466	833 (3.05 %)
Nordsjællands Hospital (2 units)	34.159	872 (2.49 %)
Bispebjerg Hospital (1 unit)	13.013	480 (3.55 %)
Glostrup Hospital (1 unit)	6.598	181 (2.67 %)
Sjællands Universitetshospital (2 units)	34.125	845 (2.42 %)
Holbæk Hospital (1 unit)	16.125	531 (3.19 %)
Slagelse Hospital (1 unit)	17.999	705 (3.77 %)
I alt	189.922	5.569 (2,9 %)

Number of unique admissions is based on the wards that are expected to participate in the study.

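### The diagnosis and surgery subgroups are defined after exposure to I-EWS or EWS has begun, so their mortality contrasts and interaction tests are not protected by randomisation

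*SAP*

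**What the plan says.** Under Subgroup analyses of primary endpoint, the SAP states: "The primary outcomes will be calculated for the following subgroups, including a test for interactions". Besides age and cluster, the groups are formed "according to the primary discharge diagnosis; cardiovascular disease, infections, pulmonary disease neurological disease, cancer and surgery done during admission". Results go into a forest plot.

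Handling of diagnoses for outcome and subgroups gives the definitions. For the registry ICD-10 codes it says "The primary diagnosis will be used when constructing". Surgical conditions are defined as "Presence of surgical procedure codes divided into different specialties (general, orthopedic, other", with no restriction to procedures done before, or planned at, admission.

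The SAP gives no alternative definition from admission data, no comparison of subgroup sizes between arms, and no caution about reading these interaction tests.

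**The concern.** A subgroup supports a causal comparison between arms when membership is settled before the intervention can act on it. Membership here is settled later. I-EWS is meant to change how often patients are scored and what follows from the score. That could affect which complications are found, which diagnosis is coded as primary, and whether a deteriorating patient is operated on. If it does so differently by arm, a subgroup holds different kinds of patients under I-EWS and EWS.

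At stake is the reading of the forest plot. An apparent harm or benefit in, say, infection or surgical patients could reflect a shift in coding or operation rates while no patient's risk of death has changed.

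**Working it through.** **1. Order of events**

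| Event | Source | Timing |
|---|---|---|
| Scoring starts | Introduction: "At admission, and as a minimum twice a day, nurses measure vital signs on all hospitalized patients" | From admission |
| Minimum stay | Patient inclusion criteria: "Admittance for more than 24 hours" | Every included patient |
| Intervention acts | Method, Intervention: "Afterwards it is possible to adjust the score by a maximum of +6 or -4" | At each scoring |
| Surgery yes/no | Handling of diagnoses | During the stay; final only at its end |
| Primary discharge diagnosis | Subgroup analyses | End of stay; for in-hospital deaths, at or after the outcome |
| Age, cluster | Subgroup analyses | Fixed at admission |

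All included patients are therefore scored before the diagnosis, and before surgery status is final.

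**2. Route from score to membership**

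The Introduction says the total score sets the interval to the next measurement and the clinical action, such as calling the doctor. I-EWS allows that score to be changed, and the main hypothesis expects fewer scores per patient per day. A path from arm to membership is thus plausible from the trial's own description. Whether it operates, and in which direction, is not stated.

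**3. What a shift could do (illustration)**

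The plan gives no figure to reproduce. Taken from Sample size calculation: 150,000 patients, split here as 75,000 per arm, and overall mortality of 2.9%. All other inputs are assumptions. No patient's risk of death is changed, and clustering is ignored.

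*Mild cases leave the subgroup under I-EWS.* Assume a subgroup of 15% (0.15 × 75,000 = 11,250 per arm) with 6.0% mortality. A fraction f of it, with 1% mortality, is coded elsewhere.

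- New risk = (0.06 − 0.01f)/(1 − f)
- f = 2%, 5%, 10% gives 6.10%, 6.26%, 6.56%: shifts of +0.10, +0.26, +0.56 points
- SE = √(2 × 0.06 × 0.94/11,250) = 0.317 points, so the shifts are about 0.3, 0.8 and 1.75 SE

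*Sicker patients enter the subgroup under I-EWS.* Let s be the subgroup share, p its mortality, f the fraction of all intervention patients who enter it, and m their mortality.

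- Subgroup risk under I-EWS = (sp + fm)/(s + f)
- Risk outside it: control (0.029 − sp)/(1 − s); I-EWS (0.029 − sp − fm)/(1 − s − f)
- Interaction z = (ln OR inside − ln OR outside)/√(sum of reciprocals of the eight expected cell counts), two-sided 0.05

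Worked case with s = 10%, p = 2.9%, f = 0.5%, m = 15%:

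- Inside: (0.0029 + 0.00075)/0.105 = 3.48%, against 2.90% under control; OR 1.21
- Outside: 0.02535/0.895 = 2.83%, against 2.90% under control; OR 0.98
- z = 2.16, so the test rejects in about 58% of trials instead of 5%

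| s | p | f | m | False difference | z | Rejection |
|---|---|---|---|---|---|---|
| 20% | 5% | 0.25% | 10% | +0.06 points | 0.36 | 6% |
| 10% | 2.9% | 0.5% | 15% | +0.58 points | 2.16 | 58% |
| 10% | 2.9% | 1% | 10% | +0.65 points | 2.44 | 69% |
| 5% | 2.9% | 1% | 15% | +2.02 points | 4.82 | nearly 100% |

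The first and last rows are the extremes of the range examined (s 5–20%, p 2.9–5%, f 0.25–1%, m 10–15%).

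**4. Would counts by arm show it?**

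In the worked case the subgroup has 0.10 × 75,000 = 7,500 patients under EWS and 0.105 × 75,000 = 7,875 under I-EWS. The SE of the difference in share is about √(2 × 0.10 × 0.90/75,000) = 0.155 points, so the 0.5-point difference is about 3.2 SE, again ignoring clustering. A net shift of that size would be visible. Equal counts would not rule out entries and exits that cancel.

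**The case against.** The strongest case on the other side is that the mechanism is possible but not shown. The escalation protocol is unchanged. The Ethics section notes that reductions are capped and that a high score still prompts more frequent observation. Scores can move either way. Only the primary diagnosis counts, so an infection found in hospital must displace the original reason for admission, and do so differently by arm. Much surgery may already be decided on arrival. The illustrative sizes are all assumed, and in the first illustration even the largest shift stays below 1.96 SE before clustering is considered.

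This stands as a limit on size and certainty. It does not restore protection by randomisation, because the definitions still depend on events after exposure and the SAP has no check.

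A reader might infer more than the document supports:

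- *That the trial's conclusion is at risk.* Overall 30-day mortality and scores per patient per day do not depend on these subgroups.
- *That a shift above 0.5 points breaches non-inferiority in a subgroup.* The margin is set for the whole trial; no subgroup margin or decision rule exists.
- *That early deaths, with less time for surgery or a specific diagnosis, bias the contrast by themselves.* This happens in both arms and matters only if I-EWS alters timing or rates.
- *That the subgroups will decide where nurses may adjust scores.* The SAP does not say so.

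**Conclusion.** The point holds, limited to the diagnosis and surgery subgroups. Their membership is determined after exposure has begun, although surgery is settled during the stay and not strictly at discharge. Their mortality contrasts and interaction tests therefore lack the protection of randomisation. The bias could be negligible or decisive, and the document does not give the differential coding or surgery rates needed to say which. The illustrated figures rest on assumed subgroup shares, mortalities and shifts, and on individual-level variances. They show what can happen, and do not predict that it will. This is a worthwhile, inexpensive improvement and not a flaw in the main analysis.

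**What to change.** - Base the subgroups that carry interaction tests on information fixed at index admission. Study variables already lists historical registry diagnoses, and also "Information regarding admissions (date, time and place of admission and discharge", which includes place of admission. The admitting diagnosis or department specialty would also serve if the extract holds it; the SAP does not list either.
- Keep the discharge-diagnosis and procedure groupings as descriptive results. Report the number and share of patients in each by arm, to show any differential coding or surgery rate.
- State that interaction tests in those groupings will not be interpreted as effect modification.

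The cost is SAP wording plus a small amount of tabulation from data already planned. The downside is that admission-based groups are less specific and do not reproduce the planned general, orthopaedic and other surgical split. Place of admission may also separate surgical from medical patients poorly, because eligible hospitals receive acute patients through an emergency department.

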The study is designed as a non-inferiority study to show that I-EWS is not inferior to the existing EWS algorithm with a non-inferiority margin (Δ) of 0.5% regarding 30-day all-cause mortality. The participating hospitals will admit 189,000 individual patients within one-year, individual sizes (admissions) are described on p.12. The sample size is based on the following assumptions: I) within a the inclusion period of ten months, the participating hospitals are expected to admit 150,000 individual patients II) mean all-cause mortality is 2.9% with variations as described on p. 11, III) a variation in mortality of 25% over the course of the year. The non-inferiority margin is set at 0.5%, and if the intervention has an effect of 0, the study has above 90% power to confirm noninferiority. In a previous cohort of 103,733 patients the mean (SD) number of scores per patient per day was 2.3 (2.0) and 15.4% of patients had one NEWS score of ≥ 6 . With the expected

inclusion, we will be able to detect a difference of 0.04 in mean number of scores and a difference of 0.6% in the number of patients with one NEWS \geq 6 with a power > 90%.

Study end

The follow-up for all patients ends after at total study period of 13 Months and is expected to end at the October 31, 2019.

Statistical plan for main outcome paper

Statistical analyses will be performed using SAS and R. Reporting of results will be in accordance with the CONSORT criteria with extension to cluster randomised trials. Analyses will be done using R. P < 0.05 will be considered statistically significant.

Consort diagram

A modified CONSORT trial profile will be used to describe patient flow and total number patients in each group and at each cluster. All patients not included in analysis will be explained.

Baseline description of groups:

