Table of summary statistics for patients and at hospital or cluster level for each group (intervention or control) will be presented with baseline variables (Number of patients, number of admissions, age, sex, Charlson Comorbidity index, hospital characteristics) Continuous variables will be summarized with: n (based on non-missing sample size), mean, standard deviation, median, interquartile range, number of missing values. Categorical variables will be reported as frequency and percentages (based on non-missing sample size) and number of missing values. Continuous and ordinal variables will be tested by Wilcoxon analysis or t-tests as appropriate for differences between groups. Categorical variables will be tested with chi-square.

Primary outcome analysis

The primary outcomes will be an **analysis of all-cause mortality and NEWS/I-EWS scores per patient per day between the intervention and control group**. Patients will be followed as one cohort and data will be analysed as randomized and in accordance with the intention-to-treat principle.

Inclusion: Patients will be included at the first admission at the participating hospitals in the study period (index admission) and will remain in this group (intervention/control) for follow-up of 30 days. Admission is defined as a contact to a hospital with a duration of more than 24 hours. All subsequent admissions (readmission) will be ignored. Any patient lost to follow-up will be censored at the last time known to be alive.

The main analysis of the primary outcome for motality will be done using logistic regression that accounts for clustering with adjustment for hospital ID, age, and sex. Intraclass correlation

coefficient with 95% confidence intervals will be reported. Results will be presented at the individual patient level. Assessment of cluster-level differences will be performed. NEWS/I-EWS scores per patient per day will be compared using linear regressions.

Each period will start with 14 days of implementation, and before cross-over patients will be followed by an observation period of 30 days Periods of implementation and observation will be censored in the analyses (patients admitted in these periods will not be included in the analyses). Cumulative incidence plots (1-survival) will be calculated using the Kaplan-Meier method and presented.

Sensitivity analyses of the primary endpoint

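### The Poisson comparison of score changes is fixed without any allowance for hospital clustering, repeated changes within a patient, or overdispersion

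*SAP*

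**What the plan says.** The whole specification is one sentence in the SAP section Additional measurements: control-arm changes from CROS values and I-EWS changes from clinical assessment "will be compared using Poisson regression models". The Endpoints section lists what is evidently the same comparison among the items reported in addition to the primary, co-primary and secondary endpoints. There, the control-arm changes are those made for temporary or chronic acceptable values.

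Two other models in the plan are described more fully. Primary outcome analysis gives mortality a "logistic regression that accounts for clustering with adjustment for hospital ID, age, and sex". Secondary endpoints gives length of stay a "linear regression following the same adjustment principles as for the primary outcome". The Poisson sentence has neither phrase. It also names no denominator, no unit of analysis and no variance method. The general significance threshold of P < 0.05 (Statistical plan for main outcome paper) makes no exception for additional measures.

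**The concern.** The randomised unit is the hospital, crossed over once. Default Poisson errors treat every change as an independent event whose variance equals its mean. Three features of this trial make that doubtful.

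- **Hospitals and wards.** Trained ambassadors teach their own wards (Method), and the plan provides for leaving out departments that did not follow the I-EWS protocol (Sensitivity analyses of the primary endpoint). The plan itself therefore expects uneven use of the modification.
- **Patients.** A patient contributes many scores. A chronic acceptable value in the control arm would plausibly alter several of them (an inference; the SAP does not say so).
- **Size.** With thousands of patients per hospital-period, the Poisson error becomes very small, so even slight variation between hospital-periods outweighs it.

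At stake is the description of how often staff change the score under each system, which is the feature that distinguishes I-EWS. Intervals that are too narrow would overstate how precisely that difference is known.

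**Working it through.** The SAP states no sample size, dispersion or intraclass correlation for this comparison, so there is no figure of its own to reproduce.

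**Inputs from the SAP**
- Eight hospitals with two periods each (Definition of clusters): 8 × 2 = 16 hospital-periods.
- "the participating hospitals are expected to admit 150,000 individual patients" (Sample size calculation): m = 150,000 / 16 = 9,375 patients per hospital-period on average. Hospital sizes are unequal.
- Significance at 0.05; two-sided is assumed here, because the SAP does not say.

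**Assumed input**
- d, the within-period minus the between-period intraclass correlation of score changes: 0 to 0.01.

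**Step 1: clustering alone.** In a cluster crossover the variance is inflated by about DE = 1 + (m − 1) × d. The true standard error is √DE times the model-based one, and the actual error rate is 2 × [1 − Φ(1.96 / √DE)].

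| d (assumed) | DE | √DE | Actual error at nominal 5% |
|---|---|---|---|
| 0 | 1.00 | 1.00 | 5.0% |
| 0.0001 | 1 + 9,374 × 0.0001 = 1.94 | 1.39 | 15.9% |
| 0.0005 | 5.69 | 2.38 | 41.1% |
| 0.001 | 10.37 | 3.22 | 54.3% |
| 0.01 | 94.74 | 9.73 | 84.0% |

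**Step 2: what such values of d mean.** For counts with mean μ per patient and Poisson variance, d is about μ × CV², where CV is the relative variation of the rate between hospital-periods within a hospital. With an assumed μ of 0.5 changes per patient, d = 0.0001 corresponds to CV = √(0.0001 / 0.5) = 1.4%, and d = 0.001 to √(0.001 / 0.5) = 4.5%. These are small variations.

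**Step 3: simulation.** The setting was 8 hospitals × 2 periods, 9,375 patients each, μ = 0.5, no true effect and 1,000 runs per setting.

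| SD of log rate between hospital-periods | Model-based Poisson | Paired t test on hospital log rates |
|---|---|---|
| 0 | 5% | 5% |
| 0.02 | 26% | 4% |
| 0.05 | 59% | 4% |
| 0.10 | 79% | 6% |

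The formula agrees. At SD 0.05, DE = 1 + 9,375 × 0.5 × 0.0025 = 12.7, √DE = 3.57, and the error is 2 × [1 − Φ(1.96 / 3.57)] = 58%. Strong heterogeneity between patients alone (frailty variance 2, no hospital-period variation) gave 18% for the Poisson test and 6% for the paired test.

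**Step 4: the only dispersion figure in the SAP.** Sample size calculation reports that "the mean (SD) number of scores per patient per day was 2.3 (2.0"). The ratio of variance to mean is 2.0² / 2.3 = 1.74, and √1.74 = 1.32. Taken alone, this gives an error of 2 × [1 − Φ(1.96 / 1.32)] = 13.7%. It describes the number of scores, not changes to scores. It is also a daily rate, so the ratio depends on the time unit: over an assumed 4-day stay it would be 4.0 / (2.3 / 4) = 6.96. It is no more than a sign that counts in this setting need not be Poisson, and the conclusion does not rest on it.

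**The case against.** The strongest reply is that the sentence merely names a model family. Poisson regression is compatible with robust, quasi-Poisson, GEE or mixed versions, and terse naming is the style of this plan. The co-primary is likewise only to be compared by linear regressions, with no cluster term in that sentence, and the mortality model lists no period term either. This part stands. A reader might infer that the SAP prescribes a plain Poisson model with independent patients, but the text does not say so. The contrast with mortality and length of stay concerns clustering and adjustment, not period.

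It can also be said that no dispersion or intraclass correlation for score changes is given, so the size of any error is assumed. That stands too, and the range properly begins at no error.

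Finally, the measure is additional and no decision rule depends on it. I-EWS prompts staff to reassess each score, so some difference between the arms is close to built in. This limits the importance of a p-value, but the interval around the difference is still what readers would use.

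What the reply does not remove is that an analyst who follows the sentence as written gets model-based errors that ignore the randomised unit, while clustering is written out for mortality.

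**Conclusion.** The point holds in conditional form and is minor. As written, the comparison makes no allowance for clustering by hospital, repeated changes within a patient, or overdispersion. If it is fitted with model-based errors, intervals are too narrow and p-values too small whenever modification rates vary between hospital-periods. The error rate is about 16% to 54% for an assumed intraclass correlation difference of 0.0001 to 0.001, and 5% if there is neither such variation nor overdispersion. These figures rest on the SAP's expected 150,000 patients, equal hospital-periods and a two-sided test.

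A reader might go further and conclude that the intervals are bound to be far too narrow, or that almost any difference will be declared significant. The SAP does not support this: it contains no variance figure for score changes and does not rule out a robust or mixed fit. The primary and co-primary conclusions do not depend on this comparison.

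**What to change.** Replace the sentence under Additional measurements with a full specification, in one of two forms.

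1. A count model with log(number of scores) as offset; terms for arm, hospital and period; an overdispersion allowance (quasi-Poisson or negative binomial); and cluster-level inference with a small-sample correction for eight hospitals. With those terms, 16 − 8 − 1 − 1 = 6 degrees of freedom remain at hospital-period level. The SAP states no such inference elsewhere, so it has to be written out here.
2. A paired hospital-level analysis of the 16 hospital-period modification rates. This is simpler, and the paired test in the simulation held its error at 4% to 6%.

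The denominator should be named in either form. The number of scores per day is itself expected to differ between the arms, so a rate per score and a rate per patient-day answer different questions.

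The cost is a few lines of SAP text, a small change to the code, and wider confidence intervals. No additional data are needed, because the scores are already collected.
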